5.5.1.2 Physical Examination

All subjects will have a complete physical examination including vital signs at screening and again at the 4-week post-dosing follow up visit. Height will be recorded once at screening. Weight will be recorded at each physical exam. Any change from screening physical examination that is clinically significant and noted during follow-up will be recorded in the patient's medical record and on the CRF. Additionally, a physical exam will be conducted on the Assigned Dosage Patients at their 1 Week Follow Up visit.

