- **Study Endpoints:** The primary end point will be an assessment of the safety of L1-79 based upon reported adverse events and changes in baseline in physical examination parameters that include orthostatic blood pressure, clinical laboratory measures, and ECGs. Secondary endpoints will include an assessment of pharmacokinetics and pharmacodynamics, as well as the attending physicians assessment as quantified by the Clinical Global Impressions scale based upon

changes from baseline in various psychometric tests, including the Vineland Adaptive Behavior Scale 2nd edition (VABS II, VABS) questionnaire, the Autism Diagnostic Observation Schedule (ADOS), the Aberrant Behavior Checklist-Community (ABC-C), the Spence Anxiety Scale (SAS), the Repetitive Behavior Score – Revised (RBS-R), the Social Responsiveness Scale (SRS), as well as from their personal observations in the clinic, and anecdotally as provided by parents or caregivers over the course of this study.

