2.2 Study Objectives**2.2.1 PRIMARY OBJECTIVE**

To document the safety of L1-79 by assessing adverse events, electrocardiographic and physical examination measures, including vital signs and laboratory parameters at 2 different dose levels of L1-79.

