5.1.3 RANDOMIZED GROUP

Following the enrollment of 5 open label patients as described in the Assigned Dosage Groups, an additional 15 patients at each dose level will be randomized 2:1 to receive either active drug or placebo (2 active to each placebo patient. These patients will be treated identically to those in the Assigned Dosage Groups with 3 exceptions:

1. No pharmacokinetic samples will be drawn,
2. No EKG will be performed
3. They will not have the 1 week follow-up, just the 1 month follow up.

After being randomized to a treatment arm each patient will be assigned a study number comprised of a 2-digit site identifier and a 3-digit patient identifier as described above.

Study numbers will not be assigned until a patient is qualified and entered into the trial. Screening failures will not be assigned numbers. However, a list of screen failures and their demographic data will be maintained by the Investigator.

Patients will be enrolled and receive their first dose within 3 weeks of completing the screening procedure.

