5.7.1 TESTING AT SCHEDULED CLINIC VISITS

The following events will occur at the scheduled clinic visits during the treatment phase of the protocol by the Investigator or the appointed study staff:

- Review of the submitted VABS II caregiver form,
- Conduct a physical (screening, visit 4, and follow up visits) and review the vital signs (all visits),
- Caregivers will be questioned about Adverse Events,
- If appropriate, medication will be returned or dispensed and the medication log completed.

- A CGI-I and CGI-S assessment will be made
- An ABC-C test will be completed
- A SRS form will be completed
- An RBS-R form will be completed
- Caregiver anecdotes will be solicited and recorded
- Patient interactions with Investigator and caregiver will be noted.

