APPENDIX A: STUDY PLAN ACTIVE TREATMENT PHASE

Form #	Form Name	Screening	wk 0 Baseline	Visit					
				Wk 1	Wk 2	Wk 3	Wk 4	1 wk post dosing	4 wk FUP
	Study Day		0 ± 2	7 ± 2	14 ± 2	21 ± 2	28 ± 2	35 ± 2	56 ± 2
1	Date of Visit	x	x	x	x	x	x	x	x
2	Informed Consent & Study Compliance agreement	x							
3	Demography	x							
4	Additional Patient Information	x							
5	Inclusion Criteria	x							
6	Exclusion Criteria	x							
7	Eligibility Criteria	x							
8	Medical history	x							
9	Family History	x							
10	Lab - Hematology (all patients)	x					x		x
11	Lab- Serum Chemistry (all patients)	x					x		x
12	Urine Analysis (all patients)	x					x		x
13	Lab - Hematology (Assigned patients only)		x*	x	x	x	x	x**	x
14	Lab- Serum Chemistry (Assigned patients only)		x*	x	x	x	x	x**	x
15	Urine Analysis (Assigned patients only)		x*	x	x	x	x	x**	x
16	PK/PD		x*	x	x	x	x		
17	Blood Draw	x					x	x**	x
18	Vital Signs - screening	x							
19	Vital Signs		x	x	x	x	x	x**	x
20	Physical Examination	x						x**	x
21	Randomization		x						
22	ADOS	x					x		
23	EKG (Assigned patients only)		x	x	x	x	x	x**	x
24	ADI-R (Telephonic)	x							
25	SAS		x					x**	x
26	VABS II		x				x	x**	x
27	ABC-C (all scales)		x	x	x	x	x	x**	x
28	SRS		x	x	x	x	x	x**	x
29	RBS-R		x	x	x	x	x	x**	x
30	CGI-S		x	x	x	x	x	x**	x
31	CGI-I			x	x	x	x	x**	x
32	CGI-Overall score		x	x	x	x	x	x**	x
33	Study Drug dispensing	x		x					
34	Study Drug Administration			x	x	x	x		
35	Drug Accountability				x		x		
36	Adverse Event		x	x	x	x	x	x**	x
37	Prior and Concomitant Medication	x	x	x	x	x	x	x**	x

*At baseline visit for Assigned Group Patients PK samples are to be taken before, and 1 hour after, the 1st dose. ** Assigned Group Patients Only

This schedule describes the study events for each patient on each study day where action is required.

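### Physical examination is part of the primary safety endpoint, but the visit schedule records no examination or weight during dosing, and section 5.7.1 contradicts that schedule

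*Combined protocol and SAP*

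**What the plan says.** The primary objective (2.2.1) is "To document the safety of L1-79 by assessing adverse events, electrocardiographic and physical examination measures, including vital signs and laboratory parameters". The synopsis bases the primary endpoint on "reported adverse events and changes in baseline in physical examination parameters that include orthostatic blood pressure, clinical laboratory measures, and ECGs". Section 6.1.4 plans tables and graphs of change from baseline in physical examination but names no visit for the comparison.

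On timing, section 5.5.1.2 says "All subjects will have a complete physical examination including vital signs at screening and again at the 4-week post-dosing follow up visit". It adds one exam for the Assigned Dosage patients at their 1-week follow-up and says "Weight will be recorded at each physical exam". Section 5.5.1.3 defines vital signs as orthostatic blood pressure, heart rate and respiratory rate, so weight is not collected with them. Section 3.2.1 puts the exam on either side of active treatment and leaves it out of its list for weeks 1 to 4. Of the randomised patients, section 5.1.3 says: "They will not have the 1 week follow-up, just the 1 month follow up".

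Section 5.7.1, on visits in the treatment phase, says otherwise: "Conduct a physical (screening, visit 4, and follow up visits) and review the vital signs (all visits". Section 5.1.4 and Appendix B give placebo patients who roll over to open-label L1-79 exams at Weeks 2 and 4 of that treatment.

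**The concern.** A component of the primary safety endpoint should be measured at least once while patients are exposed, and in the groups that allow a comparison with placebo. As scheduled, the randomised comparison of exam findings and weight is made when nobody has taken L1-79 for about four weeks. A change that appears on drug and resolves after stopping would show in those tables as no change, and the result could be read as reassurance about treatment.

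The contradiction adds a practical problem. A site working from Appendix A would not examine patients during dosing, while a site working from 5.7.1 would. On-drug exam data would then exist at some sites and not at others. Nothing missed during dosing can be collected afterwards.

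**Working it through.** No power calculation applies, because section 6.1 limits the analysis to descriptive statistics. The check is a reading of the schedule with simple arithmetic.

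**1. Group sizes (synopsis, 5.1.3).** 5 + 10 + 5 + 10 + 10 = 40, which reproduces the stated N = 40. Randomised: 2 × 15 = 30, made up of 10 + 10 = 20 on L1-79 and 10 on placebo. Assigned Dosage: 5 + 5 = 10.

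**2. Where each source puts the exam.**
- 3.2.1: before and after treatment, not at weeks 1 to 4.
- 5.5.1.2: screening and the 4-week follow-up for all; the 1-week follow-up for Assigned patients.
- 5.9.2.3 to 5.9.2.6 (Weeks 1 to 4): vital signs, no exam.
- 5.9.2.7: an exam for Assigned patients only. 5.9.2.8 (Day 56): an exam for all.
- Appendix A, form 20 ("Physical Examination"): three marks, at screening, 1 week post dosing (Assigned only) and 4-week follow-up.
- 5.7.1: screening, visit 4 and follow-up visits.

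The prose sections and the Appendix A row agree, so the gap is not an effect of how the table was extracted.

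**3. What visit 4 could mean.** By treatment week it is Week 4. Counting Day 0 as the first visit it is Week 3. Counting screening as the first it is Week 2. All three fall in the dosing phase, where every other main-phase source shows no exam.

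**4. On-drug exams and weights in randomised patients.** Under 3.2.1, 5.5.1.2, 5.9.2 and Appendix A: 0 of 30. Under 5.7.1: one each.

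**5. Time off drug at the only post-baseline exam.** Taking Day 28 as the end of dosing: 56 − 28 = 28 days. With the ±2-day windows in Appendix A, the shortest is (56 − 2) − (28 + 2) = 24 days and the longest is (56 + 2) − (28 − 2) = 32 days.

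**6. Assigned patients.** Appendix A puts their extra exam at Day 35 ± 2, nominally 35 − 28 = 7 days after dosing. Section 5.9.2.7 allows Days 28 to 35, which is 0 to 7 days.

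**7. Baseline-to-exam interval.** Sections 5.1.1 and 5.9.1 allow up to 3 weeks from screening to first dose: 3 + 8 = 11 weeks. The synopsis puts the pre-study evaluation within 1 week: 1 + 8 = 9 weeks.

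**The case against.** The strongest reply is that on-drug safety is well covered and that a before-and-after exam was intended.

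Much of the first part stands. The synopsis counts orthostatic blood pressure among the physical examination parameters, and it is taken at every visit in all patients. The primary objective likewise groups vital signs and laboratory parameters with the exam. Adverse events are elicited at Weeks 1 to 4, and laboratory samples are drawn from everyone at Week 4. Section 5.2.3.1 requires at least 2 hours of observation after the first dose, with attention to dystonias and extrapyramidal symptoms, and section 5.7 asks for investigator observations at each visit. A reader might infer that such neurological signs would go unseen. The documents do not support that: overt signs have several routes into the adverse event record. Nor do the documents name a weight effect of L1-79, so harm through missed weight change is a possibility, not an expected result.

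On intent, 3.2.1, 5.5.1.2, 5.9.2 and Appendix A do agree with one another, and 5.7.1 is the outlier. But the same group in 3.2.1 holds haematology, chemistry and urinalysis, and all three are collected from every patient at Week 4. The exam alone has no Week 4 measurement. The rollover schedule also shows that on-drug exams were considered feasible, although only in a conditional, open-label phase outside the randomised comparison.

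**Conclusion.** The point holds, confined to formal exam findings and weight. Under the schedule in 3.2.1, 5.5.1.2, 5.9.2 and Appendix A, none of the 30 randomised patients has either recorded during dosing. The placebo-controlled comparison (20 against 10) is made nominally 28 days after the last dose (24 to 32 with windows), against a baseline about 9 to 11 weeks earlier, depending on which screening limit applies. A reversible on-drug change in these measures could be missed. Section 5.7.1 contradicts the schedule.

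This rests on taking Day 28 as the end of dosing and on treating the Week 4 visit as on drug. The second assumption is supported by the samples that 5.5.1.6 times at 1 hour after dosing at each weekly visit.

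Three stronger readings are tempting but go beyond the text:
- On-drug safety is not unmeasured, for the reasons given above.
- It cannot be said flatly that none of the 40 patients is examined until at least a week off drug. The Assigned patients' extra exam may fall anywhere in Days 28 to 35 under 5.9.2.7, and 5.9.3.3, headed as the 1-week follow-up, describes patients still receiving L1-79.
- Section 5.7.1 cannot be said to require a Week 4 exam, because visit 4 is never defined.

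**What to change.** Reconcile 3.2.1, 5.5.1.2, 5.7.1, 5.9.2.6 and form 20 of Appendix A, and define visit 4. Section 3.2.1 has to be included, or it will still disagree after the others are edited.

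Record one physical exam and weight for all patients at the existing Week 4 visit, when laboratory samples are already drawn. State in the analysis plan that Week 4 is the on-drug time point for the descriptive active-versus-placebo summary of exam findings and weight, and that Day 56 is recovery. While editing, settle whether the screening limit is 1 or 3 weeks and when the Assigned patients' 1-week follow-up takes place.

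The cost is one short exam and weight per patient at a visit that already takes place, plus edits to these sections. It should be done before enrolment.

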5.5.1.3 Vital Signs

Vital signs obtained for each patient include orthostatic blood pressure (systolic/diastolic), heart rate (radial pulse) and respiratory rate at screening and all scheduled clinic visits.

5.5.1.4 Blood Pressure

Blood pressure (bp) will be taken at every visit. Orthostatic blood pressure will be assessed by recording blood pressure while sitting and then while standing in the following manner:

- Patient will sit down for 5 minutes
- Measure blood pressure and pulse rate
- Have the patient stand
- Repeat blood pressure and pulse rate measurements after standing 1 and 3 minutes

A drop in bp of ≥ 20 mm Hg, or in diastolic bp of ≥ 10 mm Hg, or experiencing lightheadedness or dizziness is considered abnormal.

5.5.1.5 Electrocardiograms

- In order to assess any possible changes in electrocardiographic variables, an EKG will be taken and read as specified in section [5.5.2](#). A pediatric cardiologist will read all EKGs.

5.5.1.6 PK Assessment

- Blood samples will be taken at baseline both before and 1h after dosing, and at each of the 4 weekly active treatment visits 1h after dosing in the Assigned Dosage Group for the purpose of measuring serum levels of L1-79.

5.5.1.7 Concomitant Medications

As documented in the history and at the screening visit, no patient currently receiving polytherapy for autism will be enrolled in this trial. Any agent which is being prescribed for the treatment of ASD will be noted as such in the eCRF. Subjects identified for accrual into this trial will be weaned to the lowest dose of any prescribed psychotropic medication over the two to four weeks preceding their screening visit deemed effective by the Investigator.

All prescription and nonprescription medication taken by the patient from 14 days prior to screening and up to and including the final visit will be recorded in the medical record and on the eCRF. Any addition, deletion, or change in the dose of these medications must be recorded.

Because the mechanism of L1-79 is the inhibition of catecholamine synthesis, the potential exists for interactions with neurologically active, and other, drugs. Investigators will be diligent in observing potential drug interactions and should appropriately reduce the dose of any concomitant medication that is observed to be potentiated in the presence of L1-79.

5.5.1.8 Clinical Laboratory Safety Assessments

The following parameters will be measured for the Randomized Groups at screening, at week 4, and at the 4-week follow-up, and in addition for the Assigned Dosage Groups at each weekly visit and the 1 Week Follow up using the central laboratory provided:

- Urinalysis
 - Color
 - Clarity/turbidity
 - pH
 - Specific gravity
 - Glucose
 - Ketones
 - Nitrites
 - Bilirubin
 - Urobilirubin
 - Blood
 - Protein
 - RBC
 - WBC
 - Squamous epithelial cells
 - Casts
 - Crystals
 - Bacteria
 - Yeast
 - Fractionated urinary catecholamines
 - Vanillylmandelic acid
- Hematology
 - hemoglobin,
 - hematocrit,
 - platelet count,
 - RBC
 - WBC with differential
- Serum Chemistry
 - sodium,
 - potassium,
 - chloride,
 - BUN,
 - creatinine,
 - AST,
 - ALT,
 - GGT,
 - LDH,
 - CO₂/bicarbonate
 - total protein,
 - albumin,
 - calcium,

- phosphorous,
- alkaline phosphatase,
- total bilirubin (direct, indirect, total),
- cholesterol,
- triglyceride,
- amylase, lipase
- T₄ & TSH
- Fractionated Plasma Catecholamines
- Metanephhrines, plasma free & fractionated.

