APPENDIX E: SAMPLE COLLECTION METHODS.....		58
APPENDIX F: DSM-5 DIAGNOSTIC CRITERIA FOR AUTISM SPECTRUM DISORDER		59

RESTRICTED DISTRIBUTION OF PROTOCOLS

- This protocol contains information that is confidential and proprietary. The information contained herein is provided for the purpose of conducting a clinical trial in collaboration with [name].
-
- The contents of this protocol may be disclosed to study personnel under your supervision and to your Institutional Review Board(s). The contents of this protocol may not be disclosed to any other parties (unless such disclosure is requested by [name]).

PROTOCOL SYNOPSIS

- Study Drug: L1-79
- Protocol Number: HT 02-121

Protocol Title: A Phase 2 Safety Study of L1-79 in the Treatment of Autism

- Study Phase: 2
- **Study Design:** This study has a dose escalating cohort design. Treatment arms consist of L1-79 at doses of 100 mg t.i.d (or placebo), or 200 mg t.i.d., (or placebo). Pharmacokinetics will be assessed in initial cohorts of 5 patients for each dose group followed by a double blinded, placebo-controlled assessment of PK/PD and safety in a cohort of 15 patients randomized 2:1 active to placebo. Groups 1& 2 below can start simultaneously. While the FDA is reviewing the data from Group 1, Groups 2 and the placebo patients randomized with Group 2 will be ongoing. All 5 subjects assigned to Group 1 (100 mg L1-79) must have completed the PK portion of the study with results analyzed and accepted by the FDA before subjects in Groups 3-5 can begin treatment.
- Sample Size: N=40
 - Group 1 (n=5) 100 mg L1-79 (1x100mg capsule+1 placebo capsule)
 - Group 2 (n=10) 100mg L1-79 (1x100mg capsule+1 placebo capsule)
 - Group 3 (n=5) 200 mg L1-79 (2x100 mg capsules)
 - Group 4 (n=10) 200 mg L1-79 (2x100 mg capsules)
 - Group 5 (n=10) Placebo (2 placebo capsules)

All Groups will receive the assigned study drug three-times daily.

- **Study Population:** Male subjects with autism between the ages of 13 and 21 years of age who meet the entry criteria and who are able to complete standardized measures allowing them to participate in this study.

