5.10 Discontinuation of Study Subjects

A patient may be discontinued for the following reasons:

- Non-compliance with treatment regimen or follow up requirements
- Lost to follow-up
- Patient and/or care giver requests voluntary withdrawal
- Adverse event sufficient in the opinion of the Investigator to warrant cessation of treatment
- Adverse event requiring unblinding of the patient's assigned treatment
- Investigator decision

Discontinuation for any reason will be documented in the eCRF and supporting documentation will be added to the patient file. Appropriate treatment will be provided for any disease or syndrome.

All subjects who receive a single dose, irrespective of discontinuation, will be followed for a period of 4 weeks subsequent to the first dose in order to determine whether the treatment was safe.

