5.13 Study Discontinuation Criteria

The occurrence of a grade 3 or 4 AE in any patient will result in the immediate discontinuation from this study. In the event of a grade 2 AE, the Investigator, at their discretion, may withhold treatment until the event resolves to grade 1 or less.

The Sponsor may at its discretion terminate the study as a whole if conditions warrant this action. The study site Investigator bears responsibility for orderly discontinuation of the study subjects enrolled at his/her study site.

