6.0 STATISTICAL PROCEDURES

6.1 Statistical Analysis Plan

Given the size of this initial IND study and the lack of statistical power, descriptive statistic will be used to report the results. A formal statistical plan for the study analyses will be prepared before the treatment portion of the study is completed.

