6.1.4 SAFETY

Adverse events will be coded using MedDRA and will be presented by body system and preferred term. Concomitant medications will be coded using [concomitant medication coding dictionary] and summarized by drug class and generic name.

Tables and graphs will show changes from baseline through 8 weeks of treatment and 26 weeks of follow-up in:

- Physical examination

- Vital signs
- Safety labs, including hematology and serum chemistry
- Cardiovascular changes, including orthostatic blood pressure.
- EKG changes from in the Assigned Dosage Group patients

Other safety data that will be presented include:

- Dose limiting toxicity
- Adverse events along with their severity and potential relationship to study treatment.
- Concomitant medications

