7.2.2 RANDOMIZED PATIENTS

- The pharmacist will place individual doses comprised of 2 capsules each in individual envelopes for 12 subjects (to allow for 2 dropouts) in 3 different treatment groups in the following manner:

- Each dose is comprised of 2 capsules to maintain a double-blind. They are distributed as:
 - Placebo group: 2 placebo capsules
 - 100 mg group: 1 x 100 mg capsule and 1 x placebo
 - 200 mg group: 2 x 100 mg capsule
- For 2 weeks of daily dosing, each patient would receive $3 \times 14 = 42 + 2$ extra doses for a total of 44 doses, each dose will be individually packaged in envelopes. The envelopes will be placed in a cardboard box
- Since 2 weeks is the limit for how much drug the FDA guidelines will allow study materials to be packaged in this manner, this process would have to be repeated twice at each study site.
- Because of the double-blind nature of the trial, each box is labeled with a sticker that has the study number and patient study number which derives from a random code that links study numbers with dosage groups.

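### Randomised patients who stop study drug before Week 4 have no scheduled on-drug safety laboratory value, and the analysis does not separate their later off-drug samples from on-drug ones

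*Combined protocol and SAP*

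**What the plan says.** Laboratory measures belong to the primary safety endpoint (Synopsis, 2.2.1, 3.2.1). Section 6.1.4 lists "Safety labs, including hematology and serum chemistry" among the changes from baseline to be shown.

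The only placebo-controlled data come from the randomised part, where "an additional 15 patients at each dose level will be randomized 2:1 to receive either active drug or placebo" (5.1.3). For these patients section 5.5.1.8 reads: "The following parameters will be measured for the Randomized Groups at screening, at week 4, and at the 4-week follow-up". Appendix A and the visit lists in 5.9.2.3 to 5.9.2.6 agree: safety samples at Weeks 1 to 3 are reserved for the Assigned Dosage Groups, and Week 4 is for everyone.

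Patients can come off drug at any time. Section 5.10 includes as a reason "Adverse event sufficient in the opinion of the Investigator to warrant cessation of treatment". Section 5.13 says: "The occurrence of a grade 3 or 4 AE in any patient will result in the immediate discontinuation from this study". Section 5.14 instead stops medication after such an event and allows it to resume if the investigator and the DMC agree. None of these sections, and no column of Appendix A, specifies a laboratory panel at stopping.

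Two provisions keep these patients in view. Section 5.10 follows every dosed subject for four weeks from the first dose, whether or not he has stopped. Section 6.1.1 defines the safety population as all who received at least one dose. Neither says which procedures a patient has after stopping.

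**The concern.** With one on-treatment laboratory point at the end of dosing, a randomised patient who stops earlier has no scheduled on-drug value. Some of these stops are caused by adverse events, so the missing values are not a random subset: they belong partly to the patients in whom a drug-related change would matter most.

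A later sample does not fully replace the missing one. If he attends at Day 28, the result falls in the Week 4 column although it was taken off drug. A change that reverses on stopping may have gone by then. Section 5.3 names crystalluria among the effects reported for the levo form at higher doses and calls the effects transient; the urinalysis panel in 5.5.1.8 includes crystals. A symptomless laboratory change of this kind may never be reported as an adverse event.

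**Working it through.** **Sample size.** The plan's total reproduces: 5 + 10 + 5 + 10 + 10 = 40. At each dose level 15 patients at 2:1 give 10 active and 5 placebo, so the randomised part has 10 on 100 mg, 10 on 200 mg and 2 × 5 = 10 on placebo. No alpha, power or effect size is stated, so there is no power calculation to check.

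**Time off drug.** The first dose is on Day 0, so four weeks of follow-up under 5.10 reach Day 28. Days off drug = sample day − day of last dose.

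| Last dose | Day 28 sample | Day 56 sample |
|---|---|---|
| Day 3 | 25 days off | 53 days off |
| Day 7 | 21 | 49 |
| Day 14 | 14 | 42 |
| Day 21 | 7 | 35 |

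The visit window in Appendix A shifts each figure by up to 2 days.

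**Illustration of what could be missed.** The rates here are assumptions. Let p be the true rate of an on-drug abnormality in an active group of 10, and q the share of affected patients who stop before Week 4 and so yield no on-drug value. The chance of seeing at least one on-drug abnormality is 1 − (1 − p(1 − q))^10. A draw at stopping that catches the abnormality corresponds to q = 0.

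| p | Draw at stopping | q = 25% | q = 50% | q = 75% | q = 100% |
|---|---|---|---|---|---|
| 10% | 65% | 54% | 40% | 22% | 0% |
| 20% | 89% | 80% | 65% | 40% | 0% |
| 30% | 97% | 92% | 80% | 54% | 0% |

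Example for p = 20%, q = 50%: 1 − 0.9^10 = 65%, against 1 − 0.8^10 = 89% with the draw.

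**How often the gap would arise.** No dropout rate is stated. For assumed early-stop rates of 5%, 10% and 20%, the chance of at least one early stop in a group of 10, 1 − (1 − d)^10, is 40%, 65% and 89%. The nearest figure in the documents is the packaging quantity in 7.2.2, "for 12 subjects (to allow for 2 dropouts) in 3 different treatment groups". If 2/12 = 16.7% were used as a rate, the chance would be 84%, but that figure is a supply allowance.

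**Precision.** With no abnormality seen, the one-sided 95% upper limit is 1 − 0.05^(1/n): 25.9% with 10 on-drug values, 31.2% with 8.

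**The case against.** A reader might infer that the laboratory result is a completers-only analysis that leaves out those who stop for toxicity. The documents do not support that. Section 5.10 keeps every dosed patient in follow-up to Day 28, where 5.9.2.6 takes safety samples from all patients; 6.1.1 keeps him in the safety population; and nothing in 6.1.4 restricts the tables to completers. The only text pointing the other way is the wording in 5.13 about discontinuation from the study, which conflicts with 5.10 and 5.14.

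Other points on this side also carry weight:

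- The study is declared descriptive: "Given the size of this initial IND study and the lack of statistical power, descriptive statistic will be used to report the results". There is no inferential comparison to bias, and a formal statistical plan is still to come, where handling of off-drug values could be settled.
- Adverse events are recorded at every visit, and serious cases are monitored until they resolve or their cause is established (5.11, 5.11.6), with laboratory reports filed as supporting documents (8.1).
- Ten open-label patients on the same doses have weekly panels.
- The list of three exceptions in 5.1.3 does not exempt randomised patients from weekly safety samples.

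These narrow the point without closing it. A later analysis plan cannot recover a sample that was never drawn. Adverse event reporting is not a scheduled panel. The open-label groups have no placebo comparator. Section 5.5.1.8, the visit lists and Appendix A all contradict the reading of 5.1.3 that would give weekly panels, so 5.1.3 needs reconciling with them.

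**Conclusion.** The point holds as a design gap that should be corrected. In the randomised groups, the on-drug laboratory comparison with placebo rests only on patients still dosing at Week 4. Those who stop earlier contribute off-drug values or none, and the plan neither says which nor keeps the two kinds of value apart. Because some stops are for toxicity, an acute and reversible change can be missed or understated.

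The size cannot be derived from the documents. A reader might turn the 2-in-12 quantity into a dropout rate and then into a percentage understatement. That is not supported: it is a packaging overage, the stopping reasons in 5.10 also include loss to follow-up and voluntary withdrawal, and no abnormality rates are given. Nor do the documents show that stops will be more frequent on active drug. The detection figures above show only what would follow from the assumed rates; the time-off-drug figures follow from the visit schedule.

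**What to change.** - **Section 5.10 and Appendix A:** when study drug is stopped early, bring the Week 4 safety panel (hematology, serum chemistry, urinalysis, vital signs, adverse events) forward to the time of stopping or the earliest feasible attendance. Record the days since the last dose.
- **Section 6.1.4 or the formal statistical plan:** pre-specify a short window after the last dose within which a sample counts as on-treatment. Without one, a patient who stops at home and attends later would still have no on-treatment value. Tabulate the last and the worst on-treatment values for all dosed patients, show later samples separately as off-treatment, and give the number without an on-treatment value by arm and reason.
- **Sections 5.13, 5.10 and 5.14:** reconcile them on whether patients with grade 3 or 4 events continue in follow-up. Also reconcile 5.1.3 with the laboratory schedule.

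The cost is a short amendment, some analysis-plan wording, and one unscheduled attendance for each patient who stops early. The number of patients is unchanged.
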